#### **11.3.2 Adverse Events**

##### ***11.3.2.1 Adverse Events and Serious Adverse Events***

An AE is any untoward medical occurrence in a subject participating in a clinical trial. An AE can be any unfavorable and unintended sign, symptom, or disease temporally associated with the

use of the study medication, whether or not considered related to the study medication. AEs will be collected from the time a patient signs the ICF until 30 days after the final visit. AEs occurring prior to the start of treatment will be recorded in the eCRF and shown in listings but not in tables of AEs. Only TEAEs (ie, those AEs that begin or worsen in severity after the start of treatment) will be tabulated in the AE tables and discussed in the clinical study report.

Pre-existing, known clinically significant conditions observed at screening should be recorded as medical history. Worsening of a pre-existing condition by at least 1 grade per CTCAE version 5.0 should be recorded as an AE.

The definition of AEs also includes accidental injuries, reasons for any change in medication (drug and/or dose) other than planned titration, reasons for admission to a hospital, or reasons for surgical procedures (unless for minor elective surgery for a pre-existing condition). It also includes AEs commonly observed and AEs anticipated based on the pharmacological effect of the study medication. All new laboratory abnormalities and baseline abnormalities worsening by at least 1 CTCAE grade must be recorded as an AE when clinically significant.

A TEAE is any AE occurring after start of study medication or pre-existing medical condition that worsens in intensity after start of study medication.

AEs should be recorded as diagnoses, if available. If not available, separate sign(s) and symptom(s) are recorded. One diagnosis/symptom should be entered per record.

Note that death is not an event; however, the cause of death is. An exception is the event of sudden death of unknown cause. Note that hospitalization is not an event; however, the reason for hospitalization is. Procedures are not events; however, the reasons for conducting the procedures are. In general, only the reason for conducting the procedure will be captured as an AE. If deemed necessary by the investigator, a procedure can be captured along with the reason for conducting the procedure.

An overdose or medication error is not an AE unless it is temporally associated with an unfavorable or unintended sign or symptom.

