7.1.3 Handling of Missing Data

Missing data handling rules for AE relationship to treatment and AE severity will be described in Section 7.4.1.

For efficacy endpoints, all efforts will be made to avoid missing data. If, however, it does occur, it will be handled as follows:

- If a visit has been missed and cytology cystoscopy results are available at the next visit and no disease is present, then the earlier visit will be counted as absence of disease.

This document is confidential.

- In addition, the count of absence of disease will be based on visit findings, meaning that if a patient missed a visit and at the next visit he/she experienced a recurrence, the recurrence will be counted only from the day on which evidence was provided.

Patients with CIS lesions that do not resolve by the 12-week cystoscopy will be classified as EFS events. For Kaplan-Meier analyses of EFS, they will be considered to have recurred at 1 day.

Any patient without tumor in the bladder but presence of tumor in the upper urinary tract will not be classified as failures in the CR and EFS analyses and will continue study participation.

Complete dates will be imputed from partial dates of adverse events and medications solely for the purpose of defining treatment emergence for adverse events and prior/concomitant status for medications. The imputed dates will not be presented in the listings. Dates will be defined using the hierarchy of derivations below.

Adverse events:

- For onset date:
 - If only the day part of the AE onset date is missing and occurs in the same month and year as the first dose date of study drug, the date of first dose of study drug will be used as the onset date of the AE. Otherwise, the first day of the month will be used to complete the onset date of the AE;
 - If the day and month parts of the AE onset date are missing and occur in the same year as the first dose of study drug, the date of the first dose of study drug will be used as the onset date of the AE. Otherwise, January 1st will be used to complete the onset date of the AE;
 - If the AE onset date is completely missing, the date of the first dose of study drug will be used as the onset date of the AE.
- For end date:
 - If only the day part of the AE end date is missing, the last day of the month will be used to complete the end date of the AE;
 - If the day and month parts of the AE end date are missing, December 31st will be used to complete the end date of the AE;

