 - If the AE end date is completely missing and the onset date of the AE occurs after the date of the first dose of study drug, the date of last dose plus 30 days will be used as the AE end date. If the AE end date is completely missing and the onset date of the AE occurs prior to the date of the first dose of study drug the date of the first dose of study drug will be used as the AE end date.

Medications:

- For onset date:
 - If only the day part of the medication onset date is missing and occurs in the same month and year as the first dose date of study drug, the date of first dose of study drug will be used as the onset date of the medication. Otherwise, the first day of the month will be used to complete the onset date of the medication;

This document is confidential.

- If the day and month parts of medication onset date are missing and occur in the same year as the first dose of study drug, the date of the first dose of study drug will be used as the onset date of the medication. Otherwise, January 1st will be used to complete the onset date of the medication;
- If the medication onset date is completely missing, the date of the first dose of study drug will be used as the onset date of the medication.
- For end date:
 - If only the day part of the medication end date is missing, the last day of month will be used to complete the end date of the medication;
 - If the day and month parts of medication end date are missing, December 31st will be used to complete the onset date of the medication;
 - If the medication end date is completely missing and the onset date of the medication occurs after the date of the first dose of study drug, the date of last dose plus 30 days will be used as the medication end date. Otherwise, the date of the first dose of study drug will be used as the medication end date.

The partial dates of medical history and prior treatments (BCG, Bladder cancer, systemic anti-therapy and radiotherapy) will not be imputed as they are already defined as prior to the treatment. No further imputation of partial dates to determine the pre/post treatment status is needed.

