7.4.1 Adverse Events

Adverse events will be graded according to the NCI CTCAE Version 5.0, coded using the MedDRA coding system, and displayed in tables and data listings by system organ class (SOC) and preferred term (PT).

A TEAE is any AE occurring after start of study medication or pre-existing medical condition that worsens in intensity after start of study medication and within 30 days of the last administration of study medication or is deemed to be related to study medication. AEs that occur after 30 days of the last administration of study medication and are not related to study medication will not be considered TEAEs.

All AEs occurring after the patient signs the ICF will be recorded, but only the TEAEs will be summarized in tables. AEs occurring between signing of the ICF and start of study medication will be included in separate listings from TEAEs.

If the start date of an AE is partially or completely missing, the date will be imputed using the rules specified in Section 7.1.3 to determine the treatment emergence. . The AE will be assumed to be treatment-emergent if it cannot be definitively shown that the AE did not occur or worsen during the treatment-emergent period (worst case approach).

Adverse events are summarized by patient incidence rates; therefore, in any tabulation, a patient contributes only once to the count for a given SOC or PT (i.e., the most related occurrence or the most intense occurrence). Missing relationship will be considered definitely related to BC-819.

An overall AE incidence summary table will be produced and will include:

- The number and percentage of patients reporting at least 1 TEAE
- The number and percentage of patients reporting at least 1 serious AE (SAE)
- The number and percentage of patients reporting at least 1 TEAE with toxicity grade of 3 or higher
- The number and percentage of patients reporting a TEAE leading to withdrawal of study drug

This document is confidential.

- The number and percentage of patients reporting a TEAE leading to study drug interruption
- The number and percentage of patients reporting a TEAE leading to death
- The number and percentage of patients reporting at least 1 TEAE related to treatment
- The number and percentage of patients reporting at least 1 treatment-related TEAE with toxicity grade of 3 or higher
- The number and percentage of patients reporting at least 1 treatment-related serious AE (SAE)

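### SAP 7.1.3 sets a missing onset to the first-dose date without checking a recorded end date, so for records that ended before dosing it conflicts with SAP 7.4.1 and 7.2.6, and no precedence is stated

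*SAP*

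**What the plan says.** SAP 7.1.3 completes partial dates "solely for the purpose of defining treatment emergence for adverse events and prior/concomitant status for medications". For adverse events it substitutes the first-dose date in three situations:

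- day missing: "If only the day part of the AE onset date is missing and occurs in the same month and year as the first dose date" (otherwise the first of the month);
- day and month missing: "If the day and month parts of the AE onset date are missing and occur in the same year as the first dose" (otherwise January 1st);
- nothing known: "If the AE onset date is completely missing, the date of the first dose of study drug will be used as the onset date".

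The medication rules have the same three branches, ending with "If the medication onset date is completely missing, the date of the first dose of study drug will be used as the onset date". None of the six refers to an end date. Separately, the year-only rule in the medication end-date list says that "December 31st will be used to complete the onset date of the medication".

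SAP 7.4.1 relies on these dates: when a start date is incomplete, "the date will be imputed using the rules specified in Section 7.1.3 to determine the treatment emergence". The same section defines a TEAE by occurrence or worsening after the start of study medication. It presumes emergence where the contrary cannot be established, and it places events between consent and first dose in separate listings.

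SAP 7.2.6 defines a concomitant drug as one taken on or after the first-dose date and a prior drug as one taken before it. It then sends partial medication dates to 7.1.3.

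**The concern.** Records that end before dosing can be in the database. Protocol 11.3.2.1 states that "AEs will be collected from the time a patient signs the ICF until 30 days after the final visit". Protocol Table 12.1 allows a screening window of up to 42 days, with cystoscopy, biopsy and TUR in it. Protocol 12.1 asks for medications taken within the 30 days before the screening visit.

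Take a urinary infection after a screening biopsy that resolved before Day 1, with only the month of onset recorded. If that is also the month of first dose, 7.1.3 dates the onset to Day 1, after the recorded end. A programmer who flags every onset on or after first dose will count it as a TEAE. Procedure-related events of this kind are largely urinary, and SAP 7.4.1 tabulates urinary events as a composite. A drug stopped before first dose, with its start missing, would likewise move from prior to concomitant.

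**Working it through.** The plan states no figure on this point, so the check is of the rules themselves.

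**1. The rules on single records.** Assume a first dose on 20 March 2019 (illustrative dates).

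| Onset known as | Recorded end | Onset under 7.1.3 | Result |
|---|---|---|---|
| March 2019 | 12 March | 20 March | 20 − 12 = 8 days after its own end |
| 2019 only | 25 February | 20 March | after its own end |
| nothing | 25 February | 20 March | after its own end |
| February 2019 | 25 February | 1 February | correctly before dosing |

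**2. The sections side by side, for a record known to have ended before first dose.**

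- *Adverse event.* The imputed onset in 7.1.3, to which 7.4.1 refers, makes it treatment-emergent. The TEAE definition and the separate-listing rule in 7.4.1 make it pre-treatment. The presumption sentence in 7.4.1 can be read either way. It may only add events, since it does not say that emergence is presumed only in that case. Or it may exclude an event whose end date disproves emergence.
- *Medication.* The imputed start makes it concomitant. The definition by use in 7.2.6 makes it prior. Section 7.2.6 has no presumption sentence to fall back on, and its one rule for a missing start with a known stop concerns stops on or after the last dose. The medication side is therefore less protected.

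**3. How often the substitution is triggered.** Assumptions: every first-dose date in a 365-day year, and events that both start and end 1 to 42 days before dosing, each onset/end pair weighted equally. Pairs per first-dose date: 42 × 43 / 2 = 903. Total: 365 × 903 = 329,595.

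- Day missing: 56,354 / 329,595 = 17.1%
- Day and month missing: 304,010 / 329,595 = 92.2%
- Wholly missing: 100%

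Pair weighting favours early onsets. Weighting each onset day in the 42 days equally, whenever the event ends, gives 35.0% for a missing day and 94.1% for a missing day and month. That count includes events still ongoing at first dose, which an end-date check would not change. Both weightings are assumed, and all these shares apply only to records with that pattern of missingness. The number of such records is not known.

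**4. With the end-date check.** If a known end before first dose settles the class, 0 of 329,595 are misclassified under any pattern.

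**5. Size per patient.** 1/140 = 0.71 points in the full set; 1/35 = 2.86 points in the interim tables, which report TEAEs (SAP 10.1).

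**The case against.** A reader might infer that these events and drugs are counted as treatment-emergent or concomitant. The documents do not establish that. A known end before dosing shows that the event did not occur in the treatment period, and 7.4.1 can be read to exclude it on that ground. If 7.4.1 is applied to adverse events and 7.2.6 to drugs in that way, nothing is misclassified. This part of the objection stands. What remains is that 7.1.3 gives the opposite answer and no order of precedence is stated.

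A reader might also infer that harm from screening procedures is attributed to BC-819. The documents do not support that either. Under Protocol 11.3.2.2 the investigator judges relationship to the drug and, independently, to procedures, so a misdated biopsy event enters the treatment-related tables only if judged related or if its relationship is also missing (7.4.1 then counts it as definitely related). Queries in the EDC system (Protocol 14.3) should make that double gap uncommon.

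Three further limits stand:

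- The qualifying TUR may precede consent (Protocol 9.4.1), and pre-existing conditions at screening are medical history (Protocol 11.3.2.1), whose partial dates are not imputed.
- Imputed dates are not shown in listings, and adverse event rates are not formally tested.
- Any error over-counts, which is the conservative direction for safety in a single-arm study.

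The December 31st wording is plainly a slip: it sits among the end-date rules, and the parallel adverse event rule completes the end date. It is still an operative instruction and should be corrected.

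**Conclusion.** The gap in 7.1.3 is real: all six onset branches ignore a recorded end date, and for a record that ended before dosing they can produce an impossible sequence of dates. Whether that record is then misclassified depends on which section the programmer follows, and the SAP does not say.

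The effect is confined to descriptive safety and medication tables. It requires both a missing or partial onset and an end known to precede first dose. Each affected patient adds 0.7 points in 140 or 2.9 points in 35. The total cannot be stated, because the documents give no frequency of partial dates; it is probably small. The 17% to 35% range for a missing day is illustrative and should not be read as an error rate. The CR and EFS analyses are unaffected.

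**What to change.** Place this check in SAP 7.1.3 ahead of the onset rules:

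> If the recorded end date (or the latest date compatible with a partial end date) is before the first dose, the AE is not treatment-emergent and the medication is prior only, and any imputed onset may not be later than the end date. The first-dose substitution applies only when the end date is missing or could be on or after first dose.

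Then:

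- State in 7.4.1 and 7.2.6 that this check takes precedence over the imputed onset.
- Do not use the consent date as a fallback onset for medications. Drugs taken in the 30 days before screening are recorded, so one stopped before consent would again start after its own end.
- Correct the year-only medication end rule so that December 31st completes the end date. The check needs this to find the latest date compatible with a year-only end.

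Cost: a few lines of SAP text and derivation code, and no new data.

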7.1.4 Pooling of Investigative Sites

Data from all participating centers will be pooled prior to analysis. It is anticipated that patient accrual will be spread thinly across centers and summaries of data by center would be unlikely to be informative and will not, therefore, be provided. However, a summary of treated patients by site will be produced.

7.1.5 Determination of Sample Size

Efficacy analyses will generally be conducted for all patients in the FAS, or in the case of the primary endpoint of CR rate will be based on all patients in the FAS with CIS at baseline (with or without papillary disease). The primary endpoint will be analyzed using a two-sided 95% CI for the CR rate. A total of 140 treated patients will be included in this study, and it is estimated that between 70 and 100 of these will have CIS. Assuming at least 70 patients with CIS, this sample size will provide over 95% power to detect a difference in CR rate in CIS patients of 20% and an alternative hypothesis rate of 40% using an exact binomial test with a nominal 0.05 two-sided significance level. If 100 CIS patients are treated, the power will be approximately 92% to detect a difference from 20% using an alternative hypothesis rate of 35%. The power is higher to detect differences from rates lower than 20%.

7.2 Patient Characteristics

7.2.1 Patient Disposition

The number of patients who complete the planned study treatment (through 96 weeks), are ongoing at time of analysis, and do not complete the planned study treatment (through week 96) will be summarized. Reasons for patients not completing the study treatment will be categorized as follows:

- Adverse event:
- For patients with CIS at baseline, failure to clear CIS lesions by the 12-week cystoscopy
- Recurrence: high grade NMIBC recurrence requiring discontinuation from the study

This document is confidential.

- Death from any cause (with specification of cause of death)
- Withdrawal of consent
- Loss to follow-up
- Sponsor terminated study

Patient disposition will be presented for all patients. Tabulations will include the following:

- Number of patients signed informed consent
- Number (%) of patients not dosed and reasons not being dosed
- Number (%) of patients dosed
 - Number (%) of patients completing the study
 - Number (%) of patients ongoing at the time of the database cutoff date
 - Number (%) of patients who discontinued the study and reason(s) for discontinuation

A listing of patient disposition will be generated. A listing of screen failure patients and the inclusion/exclusion criteria that were not met (i.e. reason for ineligibility) will be generated.

7.2.2 Protocol Deviations

All major protocol deviations will be summarized and listed.

7.2.3 Demographic and Other Baseline Characteristics

Demographics and other baseline characteristics will be presented for patients with CIS and overall in FAS. The following variables will be listed and summarized using both continuous and categorical descriptive statistics:

- Age
- Gender
- Ethnicity
- Race
- ECOG performance status (0, 1, 2)
- Height (cm)
- Weight (kg)
- BMI (kg/m²)

7.2.4 Treatment Exposure and Compliance

No dose reduction of BC-819 is planned and no dose adjustments are allowed in the study.

Study drug exposure will be presented cumulatively. The number of instillations received will be summarized using both continuous and categorical descriptive statistics (e.g., mean and frequency). In

This document is confidential.

addition, the total number of induction instillations received, the total number of maintenance instillations received, the number of patients with at least 1 missed dose (along with the median number and range of the number of missed doses in these patients), and the number of patients with missed dose due to AE will be summarized.

All dosing data will be presented in a data listing.

7.2.5 Prior Cancer Therapies

The following prior therapies will be tabulated

- Time from initial NMIBC diagnosis
- Number of prior BCG induction courses (with or without maintenance courses)
- Number of prior NMIBC occurrences (initial diagnosis + recurrences)
- Number of prior BCG instillations (total)
 - Number of induction instillations of prior BCG
 - Number of maintenance instillations of prior BCG
- Number of prior BCG instillations (most recent course)
 - Number of induction instillations of most recent BCG course
 - Number of maintenance instillations of most recent BCG course
- Other non-BCG prior bladder cancer therapy overall and by type (ie, MMC or gemcitabine)
- Number with prior systemic anti-cancer therapy
- Tumor staging at study entry
 - CIS alone (i.e., not papillary)
 - CIS with any papillary
 - CIS with any HG T1
 - CIS with HG Ta and no HG T1
 - CIS with LG Ta or T1 and no HG T1 or HG Ta
 - HG Papillary alone (i.e., not CIS)
 - Any HG T1
 - HG Ta and no HG T1
- Time from last BCG administration to diagnosis of current recurrence of NMIBC

All collected information for the diagnosis of history of bladder cancer, prior BCG, other prior bladder cancer therapy (non-BCG), prior systemic anti-cancer therapy, prior radiotherapy (related to study indication), and prior surgery (related to study indication) will be provided in by-patient data listings.

This document is confidential.

7.2.6 Prior and Concomitant Medications

Patients may not receive other therapy for bladder cancer, either intravesical or systemic, except for anticholinergic treatment and/or chronic use of corticosteroids. Patients may receive therapy for AEs per investigator judgment.

Prior medication is defined as any medication taken prior to the date first dose of study drug. Concomitant medication is defined as any medication taken on or after the date of first dose of study drug. Medications missing both start and stop dates, or having a start date prior to the first dose of study drug and missing the stop date, or having a stop date on or after the last dose of study drug and missing start date will be counted as concomitant.

The partial dates of medications will be imputed using the rule specified in Section 7.1.3. to determine the prior and concomitant status.

Prior and concomitant medications will be coded using the WHO Drug Dictionary, and patient incidence will be tabulated by Anatomic Therapeutic Class (ATC) and preferred term (PT). Patients will be counted only once for each ATC or preferred name in the event that they have multiple records of the same ATC or preferred name in the database.

All prior and concomitant medications will be included in a by-patient data listing.

